NSAID	Non-steroidal
ODAK	Orphan Drug for Acanthamoeba keratitis
PCT	Propamidine combination therapy
PHMB	Polyhexamethylene biguanide
PP	Per protocol
PPAS	Per-protocol analysis set
SAE	Serious adverse event
SAP	Statistical analysis plan
SOC	System organ class
SDTM	Study Data Tabulation Model

LINK Medical Study ID: PSR012

Acronyms	Acronyms & Abbreviations		
U	units		
VAMS	Visual Acuity Measurement Standard		
VFQ25	25-item visual functioning questionnaire		
WHO	World Health Organization		

2 Introduction

The Orphan Drug for *Acanthamoeba* keratitis (ODAK) is a project aiming to investigate the potential of polyhexamethylene biguanide (PHMB) as a safe and effective drug for the treatment of the rare eye disease *Acanthamoeba* keratitis. This debilitating infectious disease is caused by a commonly occurring protozoan and in the absence of treatment can result in blindness. There are currently no approved drugs to treat this disease.

PHMB has received the orphan drug designation (EU/3/07/498) according to EC regulations 141/2000.

The Statistical Analysis Plan (SAP) is a complementary document to the Clinical Study Protocol and includes a more technical and detailed elaboration of the principal features of the proposed statistical analysis and presentations, and the way in which anticipated analysis problems will be handled.

If the SAP suggests changes to the principal features stated in the protocol, these should also be documented in a protocol amendment. Otherwise, it will suffice to record the changes in the SAP.

3 Study Objectives

3.1 Definitions

Clinical resolution is a clinical definition, resulting from slit lamp examination, with the following findings:

- No corneal inflammation (including subepithelial infiltrates, stromal infiltrates and oedema) that
 requires treatment, with a healed corneal epithelium and minimal punctate staining (10 dots or less
 equivalent to Grade 1 on the Oxford Scale).
- No or mild conjunctival inflammation (including bulbar injections, bulbar oedema, tarsal hyperemia): mild conjunctival inflammation is acceptable if related to other concurrent conditions such as blepharitis.
- No limbitis, scleritis or anterior chamber inflammation.
- No relapse within 30 days of discontinuing all topical and systemic therapy given for Acanthamoeba keratitis.

For regulatory and verification reasons there is an additional 60-day follow-up to exclude late relapses.

The CRR_12 is the clinical resolution rate at 12 months from randomisation and is defined as the percentage of subjects cured 30 days after discontinuing all study therapies, with 12 months of randomisation. This is the primary outcome measure. Subjects whose disease has not resolved at 12 months are considered treatment failures per protocol.

3.2 Primary Objective

The primary objective of the study is to compare the Clinical Resolution Rate (CRR) at 12 months from randomization (CRR_12) of 0.08% PHMB + placebo (Group 1), with that of 0.02% PHMB + 0.1% propamidine combination therapy (Group 2) estimating the difference in CRR_12 together with the surrounding degree of uncertainty, and to test for therapeutic superiority or non-inferiority of 0.08% PHMB monotherapy.

3.2.1 Primary Variables

The primary efficacy variable is the CRR 12.

The CRR_12 is the clinical resolution rate at 12 months from randomization and is defined as the percentage of subjects cured 30 days after discontinuing all study therapies, within 12 months of randomization.

Criteria for clinical resolution:

A subject will be considered cured if resolution or absence of all the following clinical signs is confirmed by a slit lamp examination:

LINK Medical Study ID: PSR012

- No corneal inflammation (including subepithelial infiltrates, stromal infiltrates and oedema) that
 requires treatment, with a healed corneal epithelium and minimal punctate staining (10 dots or less
 equivalent to Grade 1 on the Oxford Scale).
- No or mild conjunctival inflammation (including bulbar injection, bulbar oedema, tarsal hyperemia): mild conjunctival inflammation is acceptable if related to other concurrent conditions such as blepharitis.
- No limbitis, scleritis or anterior chamber inflammation. No relapse within 30 days of discontinuing all topical and systemic therapy given for *Acanthamoeba* keratitis.

For regulatory and verification reasons, there is an additional follow-up at Day 90 after last treatment to exclude late relapses. Subjects whose disease has not resolved at 12 months are considered treatment failures per protocol.

3.3 Secondary Objectives

Secondary objectives of this study are to obtain additional safety information on 0.08% PHMB ophthalmic solution.

Two secondary hypotheses have been specified in the protocol:

- That adverse events (AEs), and those relating to toxicity in particular, are less with PHMB 0.08% monotherapy compared to the comparator
- Time-to-cure is shorter in subjects receiving PHMB 0.08% monotherapy compared to the comparator

3.3.1 Secondary Efficacy Variables

The following secondary variables were defined in the protocol:

- Best corrected visual acuity (BCVA), i.e. the eyesight test 20/20 (6/6 in metric units; the Snellen notation)
- Corneal scarring as identified by slit lamp examination
- Ulceration severity as identified by slit lamp examination using a 2-grade scoring procedure, i.e. present or absent
- Anterior chamber inflammation as identified by ophthalmoscopy using a 4-grade scoring procedure
- EQ-5D-5L questionnaire
- VFQ25 (self-administered format) questionnaire version 2000, without optional items

In addition, Time-to-cure will be assessed. Other variables may be analysed in an explorative approach. Some disease aspects will be recorded in fields of type *Any other abnormalities? If* Yes, *Specify*. Such information will be assessed, converted to *Absent/Present* variables and analysed if sufficient numbers of occurrence are seen. Such findings will be tabulated.

3.3.2 Secondary Safety Variables

The following safety variables were defined in the protocol:

- AEs
- Clinical laboratory tests
- Intraocular pressure (IOP)
- Ophthalmoscopy
- Worsening of the corneal epithelial defect and definable inflammatory signs (development of ring abscess and hypopyon) despite >30 days of treatment with the study drug)
- Rate of subjects with a relapse of infection
- Rate of subjects requiring surgery, including amniotic membrane transplants, superficial keratectomy, application of cyanoacrylate glue, therapeutic penetrating, lamellar keratoplasty, cataract surgery, evisceration, or enucleation
- Rate of subjects requiring non-study therapies, e.g., topical steroids and NSAIDs
- Rate of subject discontinuation from study: to permit alteration of anti-amoebic therapy or for other unrelated specified reasons
- Incidence of secondary complications, such as significant corneal neovascularization, corneal scarring, corneal perforation, scleritis, secondary glaucoma, cataract, retinopathy

LINK Medical Study ID: PSR012

3.4 Hypothesis

The primary hypothesis to be tested is that the CRR_12 of subjects treated with 0.08% PHMB monotherapy, is superior, or worse by no more than an acceptable pre-defined 0.20 non-inferiority margin (Δ), compared to the CRR_12 of a 0.20 PHMB + 0.1% propamidine combination therapy, administered according to the Treatment and Follow-up Protocol described in Section 5.3, which is based on a consensus of currently clinical guidelines.

Secondary hypotheses are:

- That adverse events, and those relating to toxicity in particular, are less with PHMB 0.08% monotherapy compared to the comparator.
- That time to a cure is shorter in subjects receiving PHMB 0.08% monotherapy compared to the comparator.

Note: The estimated CRR_12 from the start of treatment is 67% for the conventional (0.02% PHMB + 0.1% propamidine) combination therapy (from the sponsor's observational, case series retrospective study 038/SI20) (63% when assuming a prevalence of late stage diseases in 38% of subjects).

4 Study Design

This is a randomised, assessor-masked, active-controlled, multiple centre, parallel-group Phase 3 study to evaluate the efficacy, safety and tolerability of 0.08% PHMB ophthalmic solution compared to the conventional 0.02% PHMB + 0.1% propamidine combination therapy in male and female subjects affected by *Acanthamoeba* keratitis.

The study is designed as a superiority study with the possibility to test for non-inferiority if the superiority hypothesis is not met, according to the requirements of the guidance from the European Agency for the Evaluation of Medicinal Products (EMA) (CPMP/EWP/482/99).²¹ The specific conditions for this outcome are described in section 7.4 of the protocol.

The study consists of an eligibility screening visit, a treatment period including short ambulant visits, and follow-up visits.

Group 1: 0.08% PHMB + placebo

Group 2: 0.02% PHMB + 0.1% propamidine combination therapy (PCT)

The study will be performed in male and female subjects affected by *Acanthamoeba* keratitis, ≥12 years of age, inclusive. The inclusion- and exclusion criteria are presented in Chapter 4 of the protocol.

5 Study Population

The study will be performed in subjects affected by Acanthamoeba keratitis.

Screening will be performed on the day of the first drug administration (Day 0), or up to two days before study drug administration. The specific inclusion and exclusion criteria can be seen in sections 4.1 and 4.2 of the protocol.

5.1 Sample Size

A total of 130 subjects affected by *Acanthamoeba* keratitis will be assigned to one of the above two treatment groups in a ratio of 1:1.

The protocol states, in section 7.6:

"From the results of the sponsor's observational, case series retrospective study 038/SI, a CRR_12 of 67% for the conventional combination therapy of PHMB 0.02% and propamidine 0.1% is expected. This figure is in the range of cure rates described in the literature. If the true difference in CRR_12 is 0.20 (Δ) (or more) in favour of PHMB monotherapy (0.08% PHMB), a total sample size of 116 subjects (allowing for 10% loss to follow-up) should give the study at least 80% power to detect superiority, with 2-sided alpha=0.10 (or equivalently 1-sided alpha=0.05).

LINK Medical Study ID: PSR012

Assuming a prevalence of late stage disease, and worse outcomes, in 38% of subjects, the expected CRR_12 in the control group will be reduced from 67% to 63%. To account for the inclusion of this group, the sample size has been adjusted to 130 subjects (allowing for 10% loss to follow-up, i.e. 116 evaluable subjects).

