4.4. Subject Completion/Withdrawal

Any subject may voluntarily discontinue the study at any time without prejudice. The investigator may elect to discontinue a subject for reasons unrelated to the study drug (e.g. failure to comply with the study protocol, missed visits etc.), for reasons related to the study drug ([serious] adverse event ([S]AE])) or in case of treatment failure. In either event, reason(s) for discontinuation should be recorded on the CRF. Possible reasons for study discontinuation include the following:

Ocular intolerance.

- (S)AEs necessitating discontinuation from the study.
- Treatment failure.
- The subject is lost to follow-up.
- Subject decision not related to an (S)AE.
- Investigator decision (specify).
- Other reason (specify).

Subjects who miss up to 1 full day of treatment within the first 5 days after starting treatment or up to 2 full days of treatment after the first 5 days of treatment should not be discontinued, but will be classified as non-compliant. Subjects will be discontinued from the study if in the opinion of the investigator drug compliance is insufficient.

If the subject discontinues, all the end-of-study visit assessments must be performed, if possible. Moreover, the investigator should ensure (as far as possible) that all used and unused study drug has been collected from the subject. The subject will exit the study and be treated at the investigator's discretion. Discontinued subjects will not be replaced.

Subjects discontinued for (S)AE(s) will be followed-up after subject's discontinuation until the event is resolved or considered medically stable by the investigator. If necessary, the investigator may schedule further visits at his/her discretion. Data collected in the period up to the end-of-study visit will be recorded in the CRF. Data collected after Day 90 following the end of treatment, and related to the (S)AE that led to discontinuation will be recorded in the subject's medical record, and in the sponsor's Safety Database.

In case a subject is lost-to-follow-up, the investigator will attempt to contact the subject (by phone, letter or e-mail) at least twice.

A subject will be considered to have completed the study if all required assessments up to and including the 90 days after end of treatment and end-of-study assessments have been completed.

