7.6. Sample Size Determination

From the results of the sponsor's observational, case series retrospective study 038/SI, a CRR_12 of 67% for the conventional combination therapy of PHMB 0.02% and propamidine 0.1% is expected.²⁰ This figure is in the range of cure rates described in the literature.^{13,22,23} If the true

difference in CRR_12 is 0.20 (Δ) (or more) in favor of PHMB monotherapy (0.08% PHMB), a total sample size of 116 subjects (allowing for 10% loss to follow-up) should give the study at least 80% power to detect superiority, with 2-sided alpha=0.10 (or equivalently 1-sided alpha=0.05).

Assuming a prevalence of late stage disease, and worse outcomes, in 38% of subjects, the expected CRR_12 in the control group will be reduced from 67% to 63%. To account for the inclusion of this group, the sample size has been adjusted to 130 subjects (allowing for 10% loss to follow-up).

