7.9.1 Primary Efficacy Variable

The main endpoint disease resolution 12 months after baseline will be assessed at each visit up to study day 365.

Clinical resolution 12 months after baseline for a patient is defined as:

The percentage of subjects cured 30 days after discontinuing all study therapies, within 12 months of randomization. A clinical resolution classification requires a Yes response to the eCRF variable CRYN question: "Was clinical resolution obtained?" at one of the study visits from day 1 up to study day 365 in combination with a response *No* to the eCRF variable RELAPYN question "Did the subject experience relapse since the last visit?" at the pursuing visits, up to the last recording of this information. There should be no relapses after (the last) clinical resolution classification. Discontinued subjects will be regarded as not cured.

For patients defined as fulfilling disease resolution within 12 months, the date of the visit at which annotated CRYN is first answered with a Yes will be used as the date of resolution. The time-to-cure secondary variable will be the number of days from randomisation to the visit where resolution was recorded.

Since it is also possible to test for non-inferiority if the superiority hypothesis is not met, additional conditions are specified (see list below) to meet the strict requirements of a non-inferiority study, making it feasible to test for non-inferiority using the results from the superiority analysis, without a further separate analysis. The 90% CI for the difference between the treatments obtained from the superiority analysis gives the necessary information. Position of the lower end of the CI relative to a pre-defined agreed 0.20 non-inferiority margin (Δ) provides the key information for making decisions (conclusions) about non-inferiority.

PHMB has received the orphan drug designation. The use of 90% CI for the difference between the two treatments is to provide a 95% lower CI limit for non-inferiority.

The additional conditions specified to make testing for non-inferiority feasible are the following:

- Pre-defined non-inferiority margin (Δ =0.20) based on both clinical and statistical considerations, i.e., chosen on the basis of external information and not chosen to fit the data.
- Analysis of the FAS and the PPAS, giving similar results with respect to p-values and CIs for the
 efficacy measure at issue.

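### The sample size removes the 10% lost to follow-up, but SAP 7.9.1 counts discontinued subjects as not cured; the power of 130 subjects is then about 71–80%, or about 84% if the planning rates already count losses as failures, and the plan does not say which

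*SAP*

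**What the plan says.** **Sizing.** Protocol 7.6 and SAP 5.1 start from a control CRR_12 of 67%. The effect is given as "If the true difference in CRR_12 is 0.20 (Δ) (or more) in favour of PHMB monotherapy", and the first step (116 subjects in total) "should give the study at least 80% power to detect superiority", "with 2-sided alpha=0.10 (or equivalently 1-sided alpha=0.05". To allow for late-stage disease, the expected "CRR_12 in the control group will be reduced from 67% to 63" per cent, and the total rises to 130. Subjects "will be assigned to one of the above two treatment groups in a ratio of 1:1", so 65 per arm. Both documents mention a 10% loss allowance. Only the SAP spells out what it means: "allowing for 10% loss to follow-up, i.e. 116 evaluable subjects".

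**Endpoint rule.** SAP 7.9.1 states: "Discontinued subjects will be regarded as not cured". Protocol 4.4 lists among the possible reasons for study discontinuation: "The subject is lost to follow-up".

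**Analysis sets.** SAP 7.2 treats subjects who do not reach the day 30 visit as dropouts from the efficacy sets. SAP 7.2.1 restricts the FAS to randomised subjects with a confirmed diagnosis and an assessed primary variable, and takes disease status from the last assessment. Protocol 7.1.1 also requires the primary variable to have been assessed. SAP 7.9 bases all efficacy evaluations on the FAS.

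**The concern.** The sizing and the endpoint rule treat the same subjects in two ways. In SAP 5.1 the lost 10% leave both numerator and denominator, and the 20-point difference is preserved among the 116 who remain. Under SAP 7.9.1 a subject lost after day 30 remains in the denominator and scores as a failure. If losses are equal in the two arms, this scales both cure rates down by the same factor and so narrows the difference between them.

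At stake is the power claim for superiority, the first test in the design. If the stated power belongs to an analysis that removes losses and the planned analysis does not remove them, a reader cannot tell what power the trial has.

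**Working it through.** **Inputs.** Control 0.63, test arm 0.63 + 0.20 = 0.83, one-sided alpha 0.05 (z = 1.645), 10% loss, 1:1 allocation, 130 randomised and 116 evaluable (SAP 5.1, protocol 7.6).

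**1. The plan's own figure.** Normal approximation for two proportions with unpooled variance:

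n per arm = [p1(1−p1) + p2(1−p2)] × (1.645 + 0.842)² / 0.20²

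- 67% v 87%: variance sum 0.2211 + 0.1131 = 0.3342, so 52 per arm, 104 in total; 104/0.9 = 115.6, giving 116.
- 63% v 83%: variance sum 0.2331 + 0.1411 = 0.3742, so 58 per arm, 116 in total; 116/0.9 = 128.9, giving 130 with equal arms.
- Power at 58 per arm: Φ(0.20/√(0.3742/58) − 1.645) = Φ(0.845) = 80.1%.

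The plan's numbers therefore reproduce, with losses removed and 63% v 83% applied to those who remain.

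**2. Reading A: 63% and 83% are rates among evaluable subjects.** Let f be the share of the 10% lost who reach day 30 and are then counted as not cured; the remainder are excluded under SAP 7.2. Assume equal loss in both arms. Then

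- analysed per arm: n = 65 × (0.9 + 0.1f)
- each cure rate is multiplied by 0.9/(0.9 + 0.1f).

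| Share of losses after day 30 (f) | n per arm | Control v test | Power (unpooled) |
|---|---|---|---|
| 0 | 58.5 | 63.0% v 83.0% | 80.4% |
| 25% | 60.1 | 61.3% v 80.8% | 77.7% |
| 50% | 61.8 | 59.7% v 78.6% | 75.3% |
| 75% | 63.4 | 58.2% v 76.6% | 73.1% |
| 100% | 65 | 56.7% v 74.7% | 71.1% |

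Last row in full: 0.9 × 0.63 = 0.567 and 0.9 × 0.83 = 0.747, a difference of 0.18. The variance sum is 0.2455 + 0.1890 = 0.4345, and Φ(0.18/√(0.4345/65) − 1.645) = Φ(0.557) = 71.1%.

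Pooled variance gives about one point less throughout (70.1% in the last row).

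**3. Reading B: 63% and 83% already count losses as failures.** No inflation is needed and all 65 per arm are analysed at 63% v 83%: Φ(0.20/√(0.3742/65) − 1.645) = Φ(0.991) = 83.9%.

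**4. What the SAP rules do with a lost subject.**

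| When lost | SAP 7.2 | SAP 7.2.1 (last status) | SAP 7.9.1 |
|---|---|---|---|
| Before the day 30 visit | out of the efficacy sets | – | – |
| After day 30, before resolution | stays in | not cured | not cured |
| After recorded resolution | stays in | cured | not cured, as a discontinued subject |

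The middle row carries the point: both rules keep the subject as a failure, whereas the sizing assumes the subject is absent. The last row is a conflict within the SAP. SAP 7.9.1 adds to it by requiring freedom from relapse only as far as relapse was last recorded.

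**The case against.** The strongest reply is that the plan need not lose any power.

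- *Early losses are excluded.* This is correct: for subjects who never reach day 30 the 116-evaluable logic is right, and if all losses were early, power would stay at about 80%. Randomised subjects later proven to have fungal or viral infection are also removed from the study, and the FAS requires a confirmed diagnosis. But treatment can run to 12 months with 90 days of follow-up after it, and nothing in the documents confines losses to the first month.
- *The rates may already include losses.* The effect is stated as a difference in CRR_12, and under SAP 7.9.1 CRR_12 counts discontinued subjects as not cured. On that reading power is 83.9%. The documents do not show how retrospective study 038/SI, the source of the 67%, counted losses. This stands, and it is why the finding is conditional. It would, however, leave the loss allowance without a purpose.
- *Lost subjects may be likely failures anyway.* If 63% and 83% are instead the rates had nobody been lost, and all the lost are scored as failures, power is 77.5% when the lost are half as likely to be cured as the others, and 80.7% when they are a quarter as likely. This too is possible, and equally unstated.

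A reader might infer that power definitely falls to some figure in the low or middle seventies. The documents do not support that: every value between 71% and 80% needs an assumed timing of losses, and Reading B lies above 80%. Nor is there an arithmetic error, since 116 and 130 both reproduce. Nor does protocol 7.6 contradict the protocol's own analysis set: the protocol has no explicit rule scoring lost subjects as not cured, and its FAS leaves out unassessed subjects. The mismatch arises in the SAP.

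**Conclusion.** The mismatch stands in conditional form. SAP 5.1 describes an analysis in which the lost 10% are absent; SAP 7.2, 7.2.1 and 7.9.1 describe one in which those lost after day 30 and before resolution are present as failures. At one-sided 5%, with equal loss in both arms and unpooled variance, 130 subjects give about 80% power if no losses fall after day 30, 75% if half do, and about 71% if all do, taking 63% and 83% as rates among evaluable subjects. If those rates already count losses as failures, the figure is about 84%. Under the reading that the inflation implies, the stated 80% holds only if essentially all losses precede day 30, which neither document says. The 71% is a lower end among these scenarios at 10% loss, not a prediction.

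**What to change.** 1. In the SAP, reconcile 7.2, 7.2.1 and 7.9.1 into one rule for subjects lost to follow-up: before day 30, after day 30 without resolution, and after recorded resolution.
2. In SAP 5.1, state whether 63% and 83% include losses as failures.
3. Restate the power of 130 subjects under that rule. If the rates do not include losses, the figure lies at about 71–80%, with the assumed timing of losses given. If they do, it is about 84% and the 10% inflation wording should go.
4. Carry the restated figure to protocol 7.6.

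This costs some text and one recalculation. No extra patients are needed; the only price is a possibly less favourable stated power.
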